## 1 Introduction

The purpose of this statistical analysis plan (SAP) is to provide details of the statistical analysis according to Section 9 of the study protocol v02 for AMG 334 Study CAMG334ADE01 dated June 6, 2019. The scope of this plan includes the primary, secondary, and exploratory analyses, which will be executed by the CRO (██████████).

### 1.1 Study design

This study uses a single-cohort, 2-treatment arm, parallel-group randomized, double-blind, double-dummy design in adult patients with episodic migraine and chronic migraine, who must be either naïve or not suitable for or could have failed up to three prophylactic treatments out of: propranolol/ metoprolol, amitriptyline, flunarizine.

The following epochs are included in the study design:

- **Screening Epoch of 2 weeks:** Required for all patients to assess initial eligibility.
- **Baseline Epoch of 4 weeks:** All patients fulfilling eligibility criteria successfully completing the Screening Epoch are invited to participate. Eligibility for randomization will be assessed based on migraine frequency and diary compliance during this epoch (migraine frequency of  $\geq 4$  and  $\geq 80\%$  eDiary compliance).
- **Double-blind, double-dummy Treatment Epoch (DBTE) of 24 weeks:** All patients completing the Baseline Epoch and fulfilling baseline eligibility criteria are invited to participate. Eligible patients will be randomized to one of two treatment arms. Double-blind treatment epoch will start with a titration phase for topiramate of a maximum of 6 weeks to determine the maximal tolerated dose and must aim to reach the recommended treatment dose of 100 mg according to the German SmPC. After the titration phase, maintenance phase will start (18 weeks). Topiramate dose has to be maintained until the end of the DBTE. Erenumab dose at beginning of the DBTE is determined patient-individually by the investigator based on the guidance provided in the SmPC and can be either 70 mg or 140 mg. Dose escalation from 70 mg to 140 mg in case of insufficient response could be considered at any time during the DBTE.

Dose reduction of topiramate and erenumab is not allowed during DBTE (Visit 101-199). After visit 199 or if the patient discontinues study drug, a one week double-blind taper off phase will follow to ensure proper down titration for topiramate.

[figure not shown]
At the end of the DBTE (24 weeks) the final assessment to address the objectives will occur.

- **Follow-Up Epoch (4 weeks)** –A Follow-Up Visit 4 weeks after last study visit (or 8 weeks after last IMP injection for discontinued patients) will be required as part of routine safety monitoring. The primary analysis will be triggered when all patients have completed their respective last visit of the double-blind treatment epoch.

End of trial will occur when the last patient completes last visit (LPLV).

Figure 1-1 Study Design

Patients will be stratified into groups according to their number of migraine days during the baseline epoch (4 - 7 vs. 8 - 14 vs.  $\geq 15$  monthly migraine days).

[figure not shown]
The study will recruit approximately 375 patients per arm (750 total) including up to a maximum of 35 patients with  $\geq 15$  monthly migraine days per arm (approx. 10 % of patients per arm). Assumptions were based on clinical studies with topiramate and erenumab.

No interim analysis is planned.

[figure not shown]
## 1.2 Study objectives and endpoints

The purpose of this study is to determine the safety and efficacy of erenumab compared to topiramate in the highest tolerated dose in patients suffering from  $\geq 4$  migraine days/month, who are naïve or not suitable for or have failed up to three prophylactic migraine treatments out of: propranolol/metoprolol, flunarizine and amitriptyline.

Objective	Endpoint
Primary	
To demonstrate the tolerability of erenumab compared to topiramate assessed by the rate of patients discontinuing treatment due to AE during the double-blind epoch of the study.	Discontinuation of treatment due to AE during the double-blind epoch of the study.
Secondary	
To evaluate the effect of erenumab compared to topiramate on the proportion of patients with at least 50% reduction from baseline in monthly migraine days.	Achieving at least a 50% reduction from baseline in MMD over the last 3 months (months 4, 5, and 6) of the double-blind epoch.
Exploratory:	

To evaluate the effect of erenumab compared to topiramate on functional impairment, as measured by the Headache Impact Test (HIT-6)	HIT-6 at week 24
To evaluate the effect of erenumab compared to topiramate on generic health-related quality of life, as measured by the Short Form-36 (SF-36 v2)	SF-36 quality of life at week 24

## 2 Statistical methods

### 2.1 Data analysis general information

The primary analysis will be conducted on all patient data after database lock (after LPLV). Analyses will be performed by [REDACTED].

SAS Version 9.2 or higher will be used for all analyses. Tables and lists will be produced by the SAS Output delivery system (ODS) as rtf document which is transferred into docx-Format to reduce size.

#### General descriptive statistical rules:

Parameters which are at least interval scaled will be tabulated by the following sample statistics: Number of non-missing data, mean, standard deviation, minimum, median, and maximum.

Parameters which are nominally or ordinally scaled will be tabulated by absolute and relative frequencies. In general, missing values are not considered for calculation of percentages (i.e., adjusted percentages are calculated) if not otherwise specified.

General information on treatment arm handling, decimal places and other output-related information will be specified in tables, figures and listing (TFLs) shells accompanying this analysis plan.

## 2.1.1 General definitions

### Study treatment

Novartis will supply the investigational medicinal products (IMP) listed below in a double-dummy setting:

#### **Verum for Test-IMP:**

- 1x Erenumab 70mg/1mL (70 mg), in pre-filled syringe, administered every 4 weeks;
- 2x Erenumab 70mg/1mL (140 mg), in pre-filled syringes, administered every 4 weeks;

Dose for erenumab is 70 mg or 140 mg throughout the trial. If the response is insufficient, dose may be uptitrated from 70 mg to 140 mg. Down titration from 140 mg to 70 mg is not allowed.

#### **Verum for Control-IMP:**

- Topiramate 25 mg and 50 mg in blisters applied according to following scheme:

##### *Titration phase (6 weeks)*

The recommended dose for Topiramate is 100 mg/day in accordance with the SmPC. The titration phase must aim to reach the recommended dose as follows:

First week: Topiramate 25 mg (1x 25 mg/day) in the evening

After first week on 25 mg, dose has to be increased weekly by up titration in 25 mg increments to the highest tolerated dose. Individual patients may maintain dose for longer than one week, if deemed necessary but all efforts should be made to achieve the recommended 100 mg dose and only if that is not deemed feasible should the patient enter the maintenance phase at a lower dose. The patient will then enter the maintenance phase with the highest tolerated dose reached within the 6 week titration phase, whereas minimal dose is 50 mg topiramate (2x 25 mg/day), intermediate dose is 75 mg (1x 25 mg and 1x 50 mg/day) and maximal and recommended dose is 100 mg (2x 50 mg/day). Starting with the 50 mg dose, patients will have to take one tablet in the morning and one in the evening. Downtitration is not allowed.

##### *Maintenance phase (18 weeks)*

Patients stay on highest tolerated dose determined during titration phase

##### *Tapering off (1 week)*

Patients taking a daily dose of 75 mg or 100 mg topiramate during the DBTE should taper off topiramate after visit 199 or when discontinuing study drug. Tapering off is performed with a daily dose of topiramate reduced by 50 mg for one week.

#### **Placebo for Test-IMP:**

- 1x Erenumab matching placebo, in pre-filled syringe, administered every 4 weeks;
- 2x Erenumab matching placebo, in pre-filled syringes, administered every 4 weeks;

#### **Placebo for Control-IMP:**

- Matching topiramate tablets for 25 mg and 50 mg in blisters

#### **Erenumab**

When not specifically specified, “erenumab” refers to the individual erenumab dose of 70 mg or 140 mg.

#### **Topiramate**

When not specifically specified, “topiramate” refers to the highest tolerated dose of topiramate.

#### **Tablets Dose Level per visit in the titration phase**

Titration phase (i.e. day 1 to week 6) tablets dose level per visit is defined as follows:

- At day 1: Dose level is equal to first dose in the study.
- At week 1 to 6: Dose level is defined as the mode of the documented doses in the interval [target date of the visit, target date of visit + 7 days].

Doses documented after date of discontinuation of double-blind treatment (i.e. tapering-off doses) are not considered for calculation of dose level in the titration phase.

#### **Migraine-specific medication**

Medication belonging to the triptan or ergotamine family.

#### **Compliance with the eDiary (daily and retro)**

The protocol requirement is 80% compliance with the eDiary (daily or retro) during baseline period. See [Appendix A: Calculation rules](#) for eDiary day calculation. Compliance with the eDiary at each month is calculated as

a number of eDiary entered in baseline period or between IMP syringe doses/ number of actual days in Baseline period or interval between IMP syringe doses\*100%

#### **Stratification factor (for randomization)**

Monthly Migraine Days (MMD) category (4 - 7, 8 - 14,  $\geq$  15 MMD) at baseline as used for randomization of patients.

#### **2.1.1.1 Study dates**

##### **eDiary Device Assignment Date**

The date on which an eDiary device is assigned to a subject for the first time after completion of initial screening, i.e. the date of baseline visit.

### **Randomization Date in DBTE**

Randomization date in DBTE is the date on which a patient is assigned to one of the two treatment arms via Interactive Response Technology (IRT).

### **First IMP Dose Date**

The first IMP dose date is the date on which a subject is administered the first dose of IMP (i.e. verum test- or control-IMP) following randomization, which may be the same day or after the randomization date. For subjects who are randomized but not dosed with double-blind IMP after randomization, first IMP Dose Date is considered missing.

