- 3 – Including prior prophylactic medication.
- 4 – Includes blood pressure, pulse and temperature.
- 5 – Patient brings to each visit for use at site
- 6 – To be completed during applicable study visits before study drug administration, where applicable.
- 7 – Should also be performed at unscheduled visits.
- 8 – SAEs will be collected after signing of the informed consent through the end of the Follow-Up Epoch (8 weeks after the last IMP injection). Non-serious AEs will be collected after randomization (Visit 101) through the end of the Follow-Up Epoch (8 weeks after the last IMP injection).
- 9 – Study drug is administered by study staff, during the applicable study visits, q.m., s.c..
- 10 – Oral study drug will be dispensed to the patient at the center during the applicable study visit for home application.
- 11 – Sites will access the Interactive Response Technology (IRT) System to register study early termination.
- 12 – Should be additionally performed at any visit if deemed necessary by the investigator due to AEs.
- 13 – Should be performed/registered by the investigator prior to dosing during DBTE.
- TD = Treatment discontinuation; PFS = Prefilled syringe; PSD = Premature subject discontinuation; X = Assessment to be recorded in the source documents and the clinical data base; S = Assessment to be recorded as source documentation only.

Table 6-2 Abbreviated schedule of assessments (ASA) for patients with Treatment Discontinuation (TD)

Visit number	V105-ASA	V108-ASA	V109-ASA	V110-ASA	V111-ASA	V199-ASA	V201-ASA ²
End of Week¹	4	8	12	16	20	24	28
Complete Physical Exam						S	
Brief Physical Exam	S	S	S	S	S		
Weight						X	X
Vital Signs ³	X	X	X	X	X	X	X
Chemistry/Hematology ¹²		X				X	X
Serum Pregnancy						X	
Urine pregnancy	S	S	S	S	S		X
ECG						X	
Clinical Outcomes (eDiary)	eDiary should be maintained						
SF-36 ⁴ (eDiary)	X	X	X	X	X	X	
HIT-6 ⁴ (eDiary)	X	X	X	X	X	X	
C-SSRS	X	X	X	X	X	X	
Concomitant Medications	X	X	X	X	X	X	X
Adverse Events ⁵	X	X	X	X	X	X	X
Serious Adverse Events ⁵	X	X	X	X	X	X	X
Follow Up Phase Completion form							X

1 – All study visit target dates are to be calculated from the Day 1 visit date, and all study procedures for a given visit should be completed in the same day.

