### **Study Day**

**Study Day 1** is defined as the first IMP dose date. For patients who are randomized but not dosed after randomization, Study Day 1 is defined as the date of randomization.

**Study Day** is defined as the number of days from Study Day 1.

*Before Study Day 1:*

$$\text{Study Day} = (\text{Date of Interest} - \text{Date of Study Day 1})$$

*On or after Study Day 1:*

$$\text{Study Day} = (\text{Date of Interest} - \text{Date of Study Day 1}) + 1$$

Therefore the day prior to Study Day 1 is -1.

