### **Baseline**

The baseline period for efficacy endpoints collected by the eDiary (e.g. monthly migraine days) is defined as the period between the eDiary device assignment date and the day prior to study day 1 (study day one is not included).

A baseline for PROs (for SF-36v2, HIT-6, BDI-II) and safety endpoints (including C-SSRS) refers to the last evaluable measurement prior to or on the study day 1.

Note: Assessments on the day of randomization are assumed to have been taken as per protocol, i.e. if the assessment should be performed before dosing, the assessment will be treated as pre-dose as per protocol. Practically, i.e. that the time part of the date/time entry will be ignored.

Exception: In case there is a protocol deviation or a comment that specifically indicates that the assessment has been taken post-dose, the assessment will not be treated as pre-dose.

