### 2.1.1.5 Safety Endpoints

Analyses on Adverse Events will be performed for the entire study without differentiating between the DBTE and Follow-up epoch. Independently, whether a patient is an ASA-patient or not, AEs will be analysed in the following analysis window:

[Study Day 1; EoS Date]

Remaining safety analyses will be performed for the DBTE and Follow-up Epoch separately. Laboratory, vital signs, ECG and C-SSRS are assessed during study visits and, therefore, will be assigned to the DBTE based on (Table 2.1.1.2-1).

Concomitant medications will be assigned to the DBTE based on the following analysis window:

[Study Day 1; Week 24 visit date if the visit was performed / MIN(EoS, study day 169) if the visit was not performed]

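### As worded, Study Day 1 can fall later for topiramate patients who take their first tablet after the Visit 101 date, which shifts their AE window and early diary intervals but not those of erenumab patients

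*SAP*

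**What the plan says.** The SAP, section 2.1.1.1, defines the first IMP dose date as the date on which a subject "is administered the first dose of IMP (i.e. verum test- or control-IMP) following randomization". Study Day 1 "is defined as the first IMP dose date". In SAP 2.1.1 the active products come under headings such as "Verum for Test-IMP", and the matching placebos are listed separately, so verum excludes placebo. The next sentence of the dose-date definition is wider: "For subjects who are randomized but not dosed with double-blind IMP after randomization, first IMP Dose Date is considered missing".

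Several derivations use Study Day 1:

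- The eDiary baseline "is defined as the period between the eDiary device assignment date and the day prior to study day 1".
- Month 1 starts on Study Day 1 and ends the day before the Week 4 syringe (Table 2.1.1.4-1). If a syringe is not received, fixed study days replace the syringe dates.
- Visit windows are in study days (Table 2.1.1.2-1).
- AEs are analysed in the window "Study Day 1; EoS Date" (2.1.1.5).

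On dosing, Protocol 5.5.4 has site staff give the syringe, active or placebo, on Day 1 in both arms. For tablets, Table 6-1 footnote 10 says: "Oral study drug will be dispensed to the patient at the center during the applicable study visit for home application". The first-week tablet is an evening dose (Protocol 5.1.1). No section fixes its calendar date.

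**The concern.** In a double-dummy trial both arms receive a syringe and tablets, so the time origin should be the same event in both. With verum as the anchor it is a supervised clinic injection in one arm and an unsupervised home tablet in the other. If the first tablet is late, only the topiramate patient's clock moves.

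This bears most on the AE tables. Tolerability is what the trial sets out to show, and the protocol collects non-serious AEs from randomization (Table 6-1 footnote 8; section 7.1). A reaction to the placebo syringe before a late first tablet would be recorded but would fall outside the analysis window. The same reaction after an erenumab syringe would be counted. The days after the placebo syringe would also count as baseline diary days.

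For late starters, someone deriving Study Day 1 must also know the arm in order to choose between the two dates.

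**Working it through.** **Inputs.** Let L be the number of calendar days from the Visit 101 syringe to the first topiramate tablet. The documents do not give L; 0 to 7 is shown as an assumption. The SAP's own definition allows the first dose to fall after the randomization date. Study days are calendar dates, and for day-of-randomization assessments "the time part of the date/time entry will be ignored". Visits are taken as on schedule, with Visit 101 as day 1 and the baseline visit on day -28 (Table 6-1).

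**SAP schedule reproduced at L = 0.** Baseline is day -28 to -1, which is 28 days. Month 1 is study day 1 to 28, which is 28 days. Month 6 is 168 - 141 + 1 = 28 days.

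**Topiramate arm at delay L.** Baseline = 28 + L days, because only its end moves. Month 1 = 28 - L days, because its end is fixed by the Week 4 syringe. The fallback span for months 4 to 6, in days counted from Visit 101, is 85 + L to 168 + L. AE dates before Study Day 1 number L.

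| L | Baseline (days) | Month 1 (days) | Fallback span, months 4-6 | AE dates outside window |
|---|---|---|---|---|
| 0 | 28 | 28 | 85-168 | 0 |
| 1 | 29 | 27 | 86-169 | 1 |
| 2 | 30 | 26 | 87-170 | 2 |
| 3 | 31 | 25 | 88-171 | 3 |
| 7 | 35 | 21 | 92-175 | 7 |

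In the erenumab arm the L = 0 row applies whenever the placebo tablet is taken.

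**Baseline MMD.** With complete diaries and m migraine days in the first 28, L = 1 gives m × 28/29 if the added day is migraine-free and (m + 1) × 28/29 if it is not.

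- m = 4: 3.86 or 4.83.
- m = 8: 7.72 or 8.69. The 50% response cut-off, half of baseline, moves from 4.00 to 3.86 or 4.34.
- At a constant daily rate r the expected value is r(28 + L) × 28/(28 + L) = 28r. Single patients move, but the average does not.

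**Visit mapping.** A visit on day d from Visit 101 gets study day d - L. The Week 4 visit (day 29) becomes 28 at L = 1 and 26 at L = 3, both inside its window of 26 to 32. At L = 7 it becomes 22, inside the Week 3 window of 19 to 25. The tightest lower margin in Table 2.1.1.2-1 is 3 days (weeks 2 to 6), so on-schedule post-baseline visits keep their label up to L = 3.

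**The two sentences of the definition.** A topiramate patient who received only the placebo syringe has no verum date. That patient was nevertheless dosed with double-blind IMP, so the rule that sets the date to missing does not apply either. The definition gives no date for this case.

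**The case against.** The strongest reply is that this is loose wording with an obvious intent. The first tablet is an evening dose, Protocol section 6 counts Visits 102 to 107 from Visit 101 to keep oral supply continuous, and the SAP treats assessments on the day of randomization as pre-dose. All of this points to a first tablet on the evening of Visit 101, in which case both arms share Study Day 1. The reference to double-blind IMP points the same way. This stands as a limit on how often the problem arises. It does not repair the rule: no section requires the tablet that evening, and the second sentence conflicts with the first without overriding it.

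The reply is also right on these points:

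- The primary endpoint comes from a flag on the Treatment Completion eCRF page (SAP 2.1.1.5), not from a study-day window.
- The stratification factor is the category used at randomization.
- Months 4 to 6 follow syringe dates when syringes are given.
- Treatment emergence is worded by first dose of study treatment, and SAP 2.1.1 lists the placebos under study treatment. On that reading an AE after the placebo syringe is treatment-emergent yet still outside the AE window, so the two rules disagree.
- Treatment codes are opened after database lock for analysis (Protocol 8.3), so the need for the code affects only work before unblinding.

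**Conclusion.** The definition contradicts itself and, read literally, makes the time origin depend on the arm. The effect is confined to topiramate patients with L of at least 1. For them the AE window opens L days late, baseline ends L days late, month 1 starts L days late, and visit windows and fallback days shift by L. When the first tablet is taken on the Visit 101 date, nothing changes. The day counts assume on-schedule visits. The secondary endpoint is touched only through baseline MMD and, for syringes not received, the fallback days.

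A reader might infer more than the documents support:

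- That the arms' windows always differ, or that baseline starts at different points. They differ only for late tablet starters, and baseline starts at eDiary assignment in both arms.
- That Study Day 1 can never be derived blind. It can whenever the first syringe and first tablet share a date.
- That the lost AEs can be counted by applying the common frequency in Protocol 3.6 (1/100 to under 1/10) to late starters. That frequency is for reactions to erenumab, not to a placebo injection, and is not tied to the first dose. No late-start rate is given either. No patient number follows.

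Severity is low: a small, one-sided error that is easy to remove.

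**What to change.** In SAP 2.1.1.1, define the first IMP dose date as the earliest date of any double-blind study medication, whether syringe or tablet, active or placebo. Use that date for Study Day 1 and every window built on it, and state in 2.1.1.5 that the first dose in the treatment-emergent definition is the same date. With the syringe given at Visit 101, L drops out. Study Day 1 then equals Visit 101 in both arms, baseline and month 1 are 28 days each on schedule, and no treatment code is needed.

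The cost is a short wording change. No new data are needed, since the SAP's exposure definitions already use first syringe and first tablet dates.

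The requirement in SAP 2.2 for an active dose to enter the FAS and SAF is a separate point about membership. It should be aligned at the same time. Otherwise a topiramate patient with only the placebo syringe would have a dosing-based Study Day 1 but belong to neither set.

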### **Last IMP Syringe Dose Date**

The last IMP syringe dose date for each subject is defined as the latest date of a syringe administration.

### **Last IMP Tablet Dose Date out of tapering off phase**

The last IMP tablet dose date out of tapering off phase for each subject is defined as the date of the last tablet administration prior to the start date of tapering off phase.

### **Last IMP Tablet Dose Date (tapering off phase included)**

The last IMP tablet dose date for each subject is defined as the date of the latest administration of a tablet.

